3.5. Trial Sites

We are working with providers of childhood flu school vaccination in Wessex, Leicester and Essex NHS England Area Teams. We will randomise schools in each of the trial local authority to one of the four trial arms. Details of the areas and providers which we are working with are given in Table 4.

Table 4. Number of schools by area, provider and target cohort.

Local Area Team	Provider	Local authority	Years in prog	Number of schools				
				Total*	Infant	Junior	Primary	Special
Leicester	Leicestershire Partnership NHS Trust	Leicester	Y1-Y6	91	9	9	66	7
		Rutland	Y1-Y6	19	0	0	17	2
		Leicestershire	Y1-Y6	241	6	6	214	10
Essex	South Essex Partnership University NHS FT	Essex	R-Y6	473	51	48	356	16
		Southend on Sea	R-Y6	37	5	5	25	2
		Thurrock	R-Y6	41	0	0	40	1
Wessex	Southern Healthcare Partnership NHS Trust	Hampshire	Y1-Y3	454	117	104	207	26
	Solent NHS Trust	Portsmouth	Y1-Y3	53	16	12	23	2
		Southampton	Y1-Y3	59	10	8	37	4
	Dorset Healthcare Uni Trust	Dorset	Y1-Y3	150	4	4	124	8
		Poole	Y1-Y3	34	8	6	16	3
	Boots UK	Bournemouth	Y1-Y3	32	2	3	26	1
	Boots UK	Isle of Wight	Y1-Y3	42	0	0	40	2
Total				1726	228	205	1191	84

*Independent schools are excluded. Data are taken from <https://www.compare-school-performance.service.gov.uk/download-data>

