3.7. Power calculations

Given that all school-based flu immunisation programmes send invitation letters to parents, even a small increase in uptake from changes to the phrasing of the letter will be worthwhile. Furthermore, given that participating areas will be sending letters to all parents of eligible children it is simpler to include all schools within a participating local authority area. Including a number of providers, which cover 13 local authorities, increases the generalisability of our research findings. We are therefore starting from the position of having potentially ~1700 schools to include in the trial. Sample size calculations are not therefore appropriate as we are not sampling from the participating areas, but rather including the full population. We can however explore the potential power of our study.

Although our allocation will be stratified by local-authority, to explore the potential power of the study we have made the crude assumption that all strata are equal (i.e. that there is no variation between local authorities). We therefore used *sampsi*

followed by the *sampclus* commands in Stata to estimate our study power. We determined the number of schools using data on schools by local authority available from Compare school and college performance website^{iv}. We used 2015/16 data provided for Leicester, Leicestershire and Rutland to estimate the average size of each cluster (i.e. average number of children in school years 1-3) (excluding schools with fewer than 20 pupils in years 1-3). The average size of cohort was 110, and we have therefore conservatively used 100 as our estimate. We used an average vaccine uptake of 63.0% (SD 16.2%) in our power calculations.

We do not have a known value for the intra-class correlation (ICC). Shackleton et al⁷ estimated that ICC values for health outcomes in adolescent children ranged from ICCs ranged from 0.01 to 0.21 depending on the outcome being measured and the country. Within Britain, ICC ranged from 0.01 to 0.15 depending on health outcome, with the highest correlation for regular smoking. These health outcomes are not directly comparable with vaccine uptake or primary school age children (for which the behaviour is actually one of the parents) but nonetheless provide an anchor point around which to explore in the absence of more relevant estimates. We used 0.025 as our basic estimate.

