We have conducted power calculations that indicate with this number of schools we would have 90% power to detect a 1% absolute increase in uptake, from 63% to 64% in children in years 1-3. The large number of schools available to us (~1700 schools), will enable us to have 90% power to detect an absolute change even if ICC is relatively high (

^{iv} Available at <https://www.compare-school-performance.service.gov.uk/download-data>

Table 5). Furthermore, we will have the power to detect our secondary outcomes e.g. uptake by year group.

It is possible, due to delays getting this project off the ground, that providers areas will need to go ahead with printing their letters before we have the approvals necessary to issue the randomisation. Our power calculations show that despite this we are likely to have sufficient schools to detect, with 90% power an absolute increase of 2% in uptake, with all but the highest estimates of ICC with just one or two providers (e.g South Essex NHS Partnership Trust, who have indicated a slightly later date for printing letters, has 451 schools. Clearly the size of the effect we have the power to detect will also depend on the impact of variation between strata in the trial (which are not accounted for in these power calculations).

Table 5. Power calculations for various scenarios, assuming no variation between strata.

Outcome	Scenario	Absolute % change able to detect	Power	ICC	Number clusters required in each arm	Total number of schools required
Primary outcome	Detecting lowest absolute effect	1%	90%	0.025	187	748
Primary outcome	Estimate of impact of ICC estimates on required minimum sample size	2%	90%	0.025	47	188
		2%	90%	0.05	81	324
		2%	90%	0.15	214	856
		2%	90%	0.25	347	1388
Secondary outcome	Analysis by individual year group (i.e. average size of the cluster 30)	2%	90%	0.025	78	312
		2%	90%	0.05	110	440
		2%	90%	0.15	240	960
		2%	90%	0.25	370	1480

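### The fallback assurance of 90% power for a 2-point increase from one or two providers is not supported: Table 5 uses an SD of about 16 points for a binary outcome, and the example's 451 schools are 551 in Table 4

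*Combined protocol and SAP*

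**What the plan says.** Section 3.7 (Power calculations) considers the case in which some areas print their letters before approvals allow randomisation. It states that there would probably still be enough schools to detect, "with 90% power an absolute increase of 2% in uptake", and that this holds "with all but the highest estimates of ICC with just one or two providers". The example is the South Essex provider, which the text says "has 451 schools". The same paragraph warns that variation between strata is not allowed for.

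Table 5, in the column "Total number of schools required", gives for a 2-point change at 90% power: 188 schools at ICC 0.025, 324 at 0.05, 856 at 0.15 and 1,388 at 0.25. Each is four times the clusters per arm (47, 81, 214, 347).

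The inputs in section 3.7 are: "We used an average vaccine uptake of 63.0% (SD 16.2%) in our power calculations"; and "The average size of cohort was 110, and we have therefore conservatively used 100 as our estimate". The base ICC is 0.025, and the highest ICC cited for Britain is 0.15. No significance level is given.

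Table 4 (section 3.5) lists three local authorities under "South Essex Partnership University NHS FT": Essex 473, Southend on Sea 37 and Thurrock 41.

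**The concern.** Section 5.1 names the timeline as the main risk to the trial, and the fallback sentence in section 3.7 is the power assurance for that risk. Three things about it do not fit.

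- The example's school count disagrees with Table 4.
- At ICC 0.15, which is not the highest value in Table 5, the printed total is larger than any one provider.
- The per-arm numbers look far too small for a binary outcome in clusters of 100 children.

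If the fallback is used, the letter comparison would go ahead on a stated power that the reduced design does not have. A result compatible with no effect could then be given more weight than it deserves.

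**Working it through.** **1. School counts (Table 4).** South Essex: 473 + 37 + 41 = 551, against 451 in the text. The other providers: Southern 454; Leicestershire 91 + 19 + 241 = 351; Dorset 150 + 34 = 184; Solent 53 + 59 = 112; Boots 32 + 42 = 74. The six sum to 1,726, which is Table 4's total.

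**2. The fallback claim against Table 5's printed totals.**

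| ICC | Schools required | Single providers that suffice | Pairs that suffice (of 15) |
|---|---|---|---|
| 0.025 | 188 | South Essex, Southern, Leicestershire | 14 |
| 0.05 | 324 | South Essex, Southern, Leicestershire | 12 |
| 0.15 | 856 | none | 2 (551 + 454 = 1,005; 551 + 351 = 902) |
| 0.25 | 1,388 | none | 0 |

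Using 451 changes no single-provider result. At ICC 0.15, 451 + 454 = 905 still suffices and 451 + 351 = 802 does not.

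**3. Reproducing Table 5.** Assume two-sided 0.05 and 90% power, so z = 1.960 + 1.282 = 3.2415. Treat the outcome as a mean with SD 16 points:

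- Children per arm = 2 × 16² × 3.2415² / 2² = 1,345.
- Design effect with 100 children per school = 1 + 99 × ICC = 3.475, 5.95, 15.85 and 25.75.
- Clusters per arm = 1,345 × design effect / 100, rounded up = 47, 81, 214 and 347.

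These match Table 5. The 1-point row (187) and the four single-year rows (78, 110, 240, 370, with 30 children) also match exactly. With SD 16.2 the same method gives 48, 83, 219 and 356, which is close. A two-proportion calculation of 63% v 65% gives 421 at ICC 0.025, so it is not the source of 47. Table 5 therefore uses about 16 points as the SD of an individual child's outcome and then inflates for clustering.

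**4. The SD of the outcome.** Vaccinated or not is binary. At 63% its SD is √(0.63 × 0.37) = √0.2331 = 0.483, about 48 points. The variance is (48.3/16)², about 9 times, the one used.

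**5. Corrected requirement.** For 63% v 65%, children per comparison group = [1.960 × √(2 × 0.64 × 0.36) + 1.282 × √(0.2331 + 0.2275)]² / 0.02² = 12,103.

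- ICC 0.025: 12,103 × 3.475 / 100 → 421 schools per group; 2 × 421 = 842 in all.
- ICC 0.05: 12,103 × 5.95 / 100 → 721 per group; 2 × 721 = 1,442 in all.
- ICC 0.15: 1,919 per group; 3,838 in all, more than the 1,726 available.

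The totals here are two groups (half v half), the more favourable contrast: a factorial main effect, not one arm against another.

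**6. Power for 2 points, half v half.** SE = √[0.4606 × (1 + 99 × ICC) / (100 × N/2)], where N is the number of schools; power = Φ(0.02/SE − 1.96); 90% detectable difference = 3.2415 × SE.

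| Schools | Power, ICC 0.025 | Power, ICC 0.05 | Detectable difference, ICC 0.025 | Detectable difference, ICC 0.05 |
|---|---|---|---|---|
| 451 | 66% | 44% | 2.7 points | 3.6 points |
| 551 | 75% | 52% | 2.5 | 3.2 |
| 902 | 92% | 73% | 1.9 | 2.5 |
| 1,005 | 94% | 77% | 1.8 | 2.4 |

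The next largest pair (454 + 351 = 805) has 89% at ICC 0.025. At ICC 0.15, 551 schools give 23% and 1,005 give 38%.

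**7. Sensitivity: if 16.2 points is the spread between schools.** The text does not label it, so this is an assumption. The implied ICC is (0.162² − 0.2331/100) / (0.2331 × 0.99) = 0.0239 / 0.2308 = 0.10. Then SE = 16.2 × √(4/N), and the 90% detectable differences are 4.9 points (451 schools), 4.5 (551), 3.5 (902) and 3.3 (1,005). Power for 2 points is 26%, 30%, 46% and 50%.

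**The case against.** The best defence of the sentence has four parts.

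- **The wording has room.** It is hedged, it speaks of one or two providers, and its reference to the highest ICCs is plural. If both 0.15 and 0.25 count as highest, South Essex alone meets Table 5's totals with 451 or 551 schools. If only 0.25 counts, two pairs still exceed 856. This stands. A reader might infer that the claim fails on Table 5's totals for every single provider; the documents do not support that, because three providers pass alone at ICC 0.025 and 0.05.
- **The factorial margin.** Section 3.10 analyses main effects, which compare half the schools with half. By Table 5's own method ICC 0.15 then needs 2 × 214 = 428 schools; 451 would give 91.5% power and 551 would give 95.8%. This also stands. It shows that the printed totals and the sentence may serve different contrasts, which the plan does not say. It does not repair the SD, and the corrected figures above already use this margin.
- **The 451 is only an example.** A reader might infer that the claim rests on it. It does not: the Table 4 count is larger and favours the plan. It is a mismatch to reconcile.
- **Section 5.1 limits the damage.** Areas that miss the print date would use one letter throughout and could still test reminders, so the shortfall falls mainly on the letter comparison. That is fair, but the letter is one of the trial's two hypotheses.

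Adjustment for provider and local authority (section 3.10) may also improve precision. The plan does not quantify the gain, and its caveat about strata does not cover the SD.

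**Conclusion.** The fallback sentence is wrong as written, mainly because of the variance behind Table 5 and only secondarily because of the school counts. With the binary variance, no single provider has 90% power for 2 points at ICC 0.025 or 0.05. Two of 15 pairs reach it at 0.025 (902 and 1,005 schools), and none at 0.05 or above. For the plan's own example, power is 75% at its base ICC and 52% at 0.05 with 551 schools, or 66% and 44% with 451.

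These figures assume two-sided 0.05, 100 children in every school, equal allocation, half v half, and no gain from adjustment or loss from unequal cluster sizes. The two-sided 0.05 is inferred from the fact that it reproduces Table 5.

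It is tempting to go further and take 16.2 points as definitely the between-school SD, which would put power for one provider at about 30%. Section 3.7 does not say what the SD describes, so that remains a sensitivity case. What can be said is that it cannot be the child-level SD of a binary outcome at 63%.

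**What to change.** In section 3.7:

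1. Reconcile 451 with the 551 in Table 4, or state which schools were left out.
2. State whether Table 5's totals serve a one-arm v one-arm contrast or a factorial main effect, and which ICCs count as highest.
3. State the significance level and what the 16.2% SD measures, and recompute with the binary variance.
4. Replace the fallback sentence with 90% detectable differences under stated assumptions. For example, on the factorial margin, unadjusted, with 100 children per school and two-sided 0.05: one provider (551 schools), about 2.5 points at ICC 0.025, 3.2 at 0.05, and 4.5 if 16.2 is the between-school SD (ICC about 0.10); the two largest pairs (902 to 1,005 schools), about 1.8 to 1.9, 2.4 to 2.5, and 3.3 to 3.5.
5. Add that adjustment for provider and local authority may improve these figures.

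The cost is protocol wording and a short recalculation. No schools are added and the design does not change; the stated fallback power becomes less favourable.

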3.8. Randomisation

Randomisation will be undertaken by PHE Behavioural Insights Team. An up-to-date list of schools will be obtained from each area (or obtained from PHE and validated by the local team). Schools will be identified by their Unique Reference Number (School URN) to create the allocation list. Randomisation will be stratified by Provider and local authority. It is unlikely that we will know in advance (i.e. at the time of randomisation) which schools have email/SMS systems. (We anticipate this to be fairly common amongst schools.) We will therefore allocate all schools, irrespective of their available system, to one of the four trial arms. Randomisation will be carried out using a randomisation tool (e.g. ralloc or random number generator with schools ranked for allocation by random number order) in Stata, or other appropriate statistical-package to one of the four arms of the trial.

3.9. Data collection

Data are collected by immunisation providers as part of the routine programme. While data on the number of vaccines administered and denominators (i.e. not including data on consent) will be submitted centrally at the end of November 2016, December 2016, January 2017 and February 2017 only the final data submission in March 2017 will provide school-level data and data on consent as well as uptake.

Many areas use a spreadsheet generated by PHE which records individual level data for local management and enables data to be cumulated to the different levels required (e.g. school, local authority) and includes data on consent. These different

cumulative levels can be submitted as required, without the inclusion of individual-level data.

School-level data by school year are routinely submitted to PHE. We will obtain final school-level data from PHE at the national level in March 2017. These data will then be linked with the allocation list for analysis using the School Unique Reference (Figure 2). We will ask providers to submit an interim school-level data extract (e.g. in November) to enable the analysis to be fully planned (i.e. statistical analysis code written) ahead of the availability of final data. This will be important to enable the timely production of results which can then inform next year's programme, however it will not be compulsory if an area is not able to provide these interim data. This analysis will be seen only by a quorum of the investigators and they will not be results released to the wider study team or beyond so as not to impact on the final uptake data. No individual-level data or Personal Identifiable Information will be collected.

Data on characteristics of the schools will be obtained from publically available sources and linked to the immunisation database. This will include data from gov.uk, Compare school and college performance website^v on characteristics such as the proportion of children on free school meals, pupils with English not as the first language, religious denomination of the school and type of school. The postcode of schools will be linked to Index of Multiple Deprivation (IMD) data to obtain a deprivation indicator, quintile or decile ranking, for the school location.

Providers will obtain data on the implementation and fidelity of any reminder message delivered by the school (in line with the Standard Operating Procedure). For schools in trial arms 1 and 3 (who will be asked to send reminder messages to parents) providers will ascertain whether schools implemented the request to send a message to parents and if so, what medium they used (SMS and/or email) and whether they altered the message. For schools in trial arms 2 and 4 (who will not be explicitly asked to contact parents) providers will ascertain whether schools sent a message to parents (before or after the invitation letter but not including mention in newsletters or similar). We anticipate that providers will collect this information during the immunisation session at the school.

[figure not shown]
Finally, given the geographical and temporal variation in immunisation flu uptake levels and variation in the use of template letters in different areas, we will collect and analyse the letters sent in non-trial areas. This will give us valuable insight into the extent to which national templates are adopted and an understanding of the variation in invitation letters. This information will inform the understanding of the analysis of the trial, with respect to understanding changes in uptake seen from year to year in non-

^v Available at <https://www.compare-school-performance.service.gov.uk/download-data>

trial areas. To collect this information we will request that areas send us a copy of their invitation letter for this year's immunisation programme. This request will most likely be sent from NHS England central team ([name] and [name] – co-investigators on this trial) asking commissioners to obtain invitation letters from their local providers).

Figure 2. Data flow from allocation list, PHE National Infection Service immunisation data and school characteristics data, with linkage through the School Unique Reference Number (URN).

Abbreviations: NIS: National Infection Service; Pn Provider

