In 2015/16 nationally, uptake in Years 1 and 2 was 53.6%.² Areas that participated in the pilot programme vaccinating primary school children (5-11 years) showed both decreasing uptake with increasing age (from 62.6% in Year 1 to 54.7% in Year 6 in 2015/16) and lower uptake last year than the previous year (57.9% compared with 60.4%). Delivery methods (school, GP or pharmacy) had considerable impact on uptake, with higher uptake in those areas that delivered flu immunisation through schoolsⁱ. Analysis has also shown that lower uptake is associated with deprivation and ethnicity.

The majority of areas offer the immunisation through school-based programmes delivered by providers that are commissioned by the NHS. Parents of eligible children are sent a letter informing them about the vaccination programme and inviting them to return the consent form for their child's vaccination. While uptake in schools is higher than GP or pharmacies, there remains approximately 30% of children for whom consent is neither given nor actively withheld.³

PHE provides template letters that immunisation providers can use. The PHE Behavioural Insights Team has worked with the NHS England and the PHE immunisation team to design the template letter for 2016/17. This letter is informed by behavioural insight theory to encourage parents to return the consent form.

There is evidence from the field of behavioural science to suggest that a low cost intervention, such as the content of an invitation letter or a reminder text message, may be effective in changing behaviour. In a previous trial run by our team, PHE Behavioural Insights Team, a 4% increase in health checks was shown by simplifying invitation letters and adding a tear-off slip where individuals could note the time and

ⁱ (55.6%, 32.9% and 16.1% uptake school, GP and pharmacy delivery respectively)

date of their first appointment, as a memory aid.⁴ Redesigning the invitation letter in combination with primer and reminder text messages increased uptake by 12% compared to the standard letter. Similar effects have been found in other non-health areas, for example, research from the Behavioural Insights Team and the DVLA showed that including an image of a person's car in their car tax collection letter increased tax payments from 40%-49%⁵ and an HMRC trial showed that providing a localised social norm message increased tax returns by 5%.⁶

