Here we set out our proposal to test whether behaviourally-informed interventions (i.e. the new template letter and SMS/email reminders) increase uptake of childhood influenza vaccination in schools, through increasing response rate. Such evidence would encourage adoption of the national template letter, which we understand many areas do not currently adopt, provide evidence for the provision of reminders and confirm whether the theory-based changes to the invitation letters have the anticipated impact.

Table 1. Target age groups for national and pilot childhood influenza immunisation programmes, by winter season.

Winter season	National programme ^a	Pilot programme ^a
2013/14	2y and 3y olds (in primary care)	4-11 year olds (reception to school year 6) eligible for vaccination in 7 geographically discrete areas.
2014/15	2-4 years of age (in primary care)	Both primary school aged children (5-11y) and secondary school aged children, 11-13y (school years 7 and 8 age) eligible for vaccination in 14 pilot areas (including pilot areas that participated in 2013/14)
2015/16	2-4 years of age (in primary care) and school years one and two (5y and 6y at 31st August)	6 pilot areas that had piloted the school based programme since 2013 to 2014 continued to offer the vaccine to all primary school age children aged 5-11 years (school years 1 to 6 age).
2016/17	2-4 years of age (in primary care) and School years 1, 2 and 3 (5, 6 and 7y at 31st August)	As in 2015/16 primary school children in years 1 to 6 in former school pilot areas will continue to be offered the vaccine.

^a Ages refer to age on 31st August/1st September of the year

2. Aims and hypothesis

The aim of this study is to investigate whether behavioural insight-informed changes to the invitation process can improve uptake of childhood flu immunisation. Our specific hypotheses are:

[figure not shown]
1. Changes to the invitation letter will increase return of consent forms and thereby increase uptake of childhood flu vaccine through schools.
2. Reminders to return the consent form will increase return of consent forms and thereby increase uptake of childhood flu vaccine through schools

3. Trial design

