3.10. Data analysis

Analysis will be undertaken by the PHE Behavioural Insights Team working with the Statistic Unit, PHE National Infection Service. Our main analysis will be by intention to treat allocation for the primary and secondary outcomes. We will use logistic regression to investigate the main effect of the interventions and their interaction. The model also will include provider, local authority and school effect to take into account extra variation that was not explained by intervention and other confounder variables. In the models, we will also investigate the impact of secondary factors such as school-year (to determine if there's any greater impact for those that have not previously

received an invitation letter) and inequalities (e.g. IMD quintile, proportion of children eligible for free school meals, proportion of children not with English as first language).

We will also undertake a per-protocol analysis of the primary and secondary outcomes, including in the analysis only those schools in trial arms 1 and 3 who implemented the request to send a reminder message with high fidelity to the request and those schools in trial arms 2 and 4 who did not send a reminder request. While the intention to treat analysis will be a composite of the effectiveness of reminders and the prevalence of SMS/email systems, the per-protocol analysis will enable these components to be disentangled.

We will analyse the invitation letters used in non-trials areas by coding the letters using the Theoretical Domains Framework (TDF). This will enable us to assess their behavioural-insight framing and fidelity to the new template letter. We will analyse whether those areas that used a letter similar to the new template had i) higher uptake and ii) greater change in uptake from to last year, compared to areas that used a dissimilar letter.

4. Study sponsorship and approvals

This study has been reviewed by the PHE Research Ethics and Governance Group to gain approval for PHE to act as the study sponsor.

Health Research Authority (HRA) approval has been sought, which includes ethical (opinion provided through UK Health Departments' Research Ethics Service), governance and legal review. (HRA/ethics number xxxxxxxx).

The trial has been registered on clinicaltrials.gov, trial number xxx.

5. Main risks and mitigation

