5.1. Timelines

The main risk to the successful implementation of this trial is meeting the timeline to enable local areas to implement the randomisation of letters component of the trial (mid-July deadline for most areas). The delay in initiating this development of the trial has been due to changes in budgets at PHE which led to a reduction and delay in the resources that could be allocated to this project. Should the trial not gain approvals in time to implement the randomisation of letters in a participating area, we will recommend that the area use the behaviour insights informed template letter for all

schools. Such areas would be invited to trial the effect of the SMS/email reminder on uptake. In the unlikely scenario of all areas being unable to participate in the letter-intervention (due to print-deadlines being ahead of approvals), the evaluation of the new template will rely on the ecological-analysis of fidelity to the new template letter in non-trial areas and uptake. While we are and will actively work with research sites to aim for this approach, if particular areas are unhappy to universally use the new template letter, we will take the above approach using the local letter updated from last year. One of the main reasons for including a large number of research sites at this stage is to give us the greatest possibility of running an effective and sufficiently powered trial, given the practical considerations.

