Appendix 2.2. Example 2 invitation letter from 2015/16 season

Southern Health **NHS**
NHS Foundation Trust

Autumn 2015

Dear Parent/Guardian,

Flu vaccination for children in Years 1 and 2

From October 2015 all children in years 1 and 2 will be offered flu vaccination through a nasal spray. This extension of the national flu immunisation programme to children is part of a phased introduction, based on the advice of independent experts.

Your child will be offered a flu vaccine that is given as a simple spray up the nose. It is painless, very quick, and side effects are uncommon. This vaccination programme is designed to protect your child against flu which can be an unpleasant illness and although rarely, sometimes causes serious complications. By having the flu vaccination, children are also less likely to pass the virus on to friends and family. This will help to protect those who are at greater risk from flu including infants, older people and those with an underlying health condition. The flu vaccine provides protection against the strains that are predicted to circulate in the coming season. These strains may change from year to year which is why we recommend vaccination every year.

A consent form and leaflet explaining the programme is enclosed.

Please complete the consent form (one for each child) and return it to the school within one week, so your child can be given the vaccine in school. Please note if the consent form is not returned your child will not be able to have the vaccine. Please contact your school, or telephone the healthcare team on [name] for the date planned for your school. For more information about the flu vaccine please see the school nurse website at:

<http://www.southernhealth.nhs.uk/health-and-wellbeing/childrens-health/flu-immunisation>

If your child becomes wheezy or has their asthma medication increased just before or on the day of the vaccination session, please contact the healthcare team on [name]

Please remember to return the consent form even if you DO NOT consent to the vaccination for your child, explaining the reason for your decision. This will help us in the development of the flu vaccination programme in the future.

Your child's school will be collecting the completed consent forms. If you would prefer to keep the information confidential please return the form in a sealed envelope addressed for the attention of the School Nurse with your child's name on the back of the envelope.

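### The non-trial-area analysis of change in uptake classifies areas on the 2016/17 letter alone, so it cannot separate areas that changed their letter from areas whose letter was already similar

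*Combined protocol and SAP*

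**What the plan says.** Section 3.9 (Data collection) describes a survey of letters outside the trial areas: "we will request that areas send us a copy of their invitation letter for this year's immunisation programme". Its stated purpose includes helping to explain year-to-year movements in uptake in those areas.

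Section 3.10 (Data analysis) codes these letters with the Theoretical Domains Framework (TDF). The exposed group is "those areas that used a letter similar to the new template". It is compared with the remainder on (i) uptake and (ii) "greater change in uptake from to last year, compared to areas that used a dissimilar letter". No cut-off for similarity is given, and nothing requires the letter to have changed since last year.

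Section 5.1 (Timelines) gives the analysis a fallback role. If no area can randomise letters, "the evaluation of the new template will rely on the ecological-analysis of fidelity to the new template letter in non-trial areas and uptake". The protocol calls that scenario unlikely.

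The only 2015/16 letters mentioned anywhere are the trial providers' own, which serve as control letters (section 3.3, Appendix 2).

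**The concern.** A comparison of changes identifies a letter effect only through areas whose letter changed. Outcome ii differences uptake over two seasons but takes the exposure from the second season only. An area with a similar letter in both seasons contributes no change in exposure, yet it is counted as exposed. An area that moved away from a similar letter is counted as an unexposed comparator although its exposure fell.

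The documents make some persistence plausible. Section 5.2 reports that local teams are often unwilling to alter their letters much between seasons. The 2015/16 letter in Appendix 2.2 already describes "flu which can be an unpleasant illness and although rarely, sometimes causes serious complications", which is close to a sentence in the Appendix 1 template.

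What is at stake is interpretation. A small or null result on outcome ii could mean that the template does little, or that many similar areas had nothing to change. The data as planned could not tell these apart.

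**Working it through.** The documents give no sample size, power or effect size for the non-trial-area analysis, so there is no figure of the plan's to reproduce. The check is algebraic.

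**Inputs**

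- Exposure: similarity of the 2016/17 letter to the template (sections 3.9 and 3.10).
- Outcome ii: uptake in 2016/17 minus uptake in 2015/16 (section 3.10).
- e: the effect on uptake of a similar rather than a dissimilar letter, assumed additive and constant over areas and seasons. For scale, e = 2 percentage points is borrowed from the power scenarios in section 3.7. The documents do not set it for this analysis.
- f: share of areas classed similar this year whose letter was also similar last year. Not in the documents; range 0 to 0.75 assumed.
- g: share of areas classed dissimilar this year whose letter was similar last year. Not in the documents; 0 in the main illustration.

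**Derivation**

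1. Similar group: mean exposure goes from f to 1, so the expected letter-related change in uptake is e × (1 − f).
2. Dissimilar group: mean exposure goes from g to 0, so the expected change is −e × g.
3. The contrast is e × (1 − f) − (−e × g) = e × (1 − f + g).

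**Results**

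When g = 0, keeping the same power with equal variances needs 1/(1 − f)² times as many areas.

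| f | g | 1 − f + g | Contrast if e = 2 points | Areas needed, multiple |
|---|---|---|---|---|
| 0 | 0 | 1.00 | 2.0 | 1.00 |
| 0.10 | 0 | 0.90 | 1.8 | 1.23 |
| 0.25 | 0 | 0.75 | 1.5 | 1.78 |
| 0.50 | 0 | 0.50 | 1.0 | 4.00 |
| 0.75 | 0 | 0.25 | 0.5 | 16.00 |
| 0.25 | 0.25 | 1.00 | 2.0 | – |
| 0.10 | 0.25 | 1.15 | 2.3 | – |

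The last two rows show that the error can also cancel (f = g) or reverse (g greater than f).

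**With both letters coded**

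If areas that moved from dissimilar to similar are compared with areas dissimilar in both seasons, the expected changes are e and 0. The contrast is then e whatever f and g are, other confounding aside.

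**The case against.** The strongest reply is that the template was new for 2016/17, so no area could have used it the year before, and that no document shows a non-trial area with a similar letter in 2015/16. Appendix 2.2 is weak evidence on this. It is a trial-area provider's letter, offered as an example of a control letter. Of the seven phrasing features in Table 2 it lacks three: the headline that the annual vaccination is due, the statement that it is free, and the social norm. It is also longer than the template. All of this is correct, and it means that f may be small. It does not remove the point, because exposure is defined by similarity to the template, with no cut-off, and the plan collects nothing that would show whether f is small.

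Four stronger readings are tempting, and the documents do not support them.

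- *The whole non-trial-area analysis is undermined.* For outcome i, uptake this year, this year's letter is the right exposure.
- *The letter evaluation would rest on this analysis as soon as print deadlines slip.* Section 5.1 says so only if every area is unable to randomise letters, and calls that unlikely. Section 3.7 adds that one or two providers would probably suffice to detect a 2-point increase at all but the highest intra-class correlations.
- *The added year group biases the comparison.* Table 1 gives the national 2015/16 target as "2-4 years of age (in primary care) and school years one and two (5y and 6y at 31st August"; Year 3 was added in 2016/17. A shift common to both groups cancels. It biases the contrast only if programme coverage differs between the groups, which the documents do not show. Section 3.9 says school-level data by school year are routinely submitted, so the years can be matched.
- *Delivery route creates a gap of known size.* Footnote i reports "55.6%, 32.9% and 16.1% uptake school, GP and pharmacy delivery respectively", so route matters for uptake. Any bias in points would need the split of routes between similar and dissimilar areas, which is not given. A fixed difference in level between routes also drops out of the change comparison.

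**Conclusion.** The point holds for outcome ii only. As planned, the contrast estimates e × (1 − f + g) rather than e, with f and g unknown and not measurable from the data to be collected. If no dissimilar area had a similar letter last year, a quarter of similar areas already similar reduces the contrast to 0.75e, and a half reduces it to 0.5e. If f = g there is no net bias, and if g is larger than f the effect is overstated. This rests on an additive letter effect that is constant over areas and seasons. The shares are illustrations, not estimates, so the actual size and direction cannot be stated.

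The randomised comparison is untouched. This is a cheap improvement to a supplementary analysis. It would carry real weight only in the scenario where no area can randomise letters.

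**What to change.** In section 3.9, ask each non-trial area, in the same request, for its 2015/16 letter as well as its 2016/17 letter, and for its delivery route.

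In section 3.10:

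- code both letters with the same TDF scheme;
- for outcome ii, relate change in uptake to change in similarity to the template;
- use the year groups offered in both seasons (Years 1 and 2);
- restrict to areas with school delivery, or adjust for route.

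Outcome i can keep this year's letter as its exposure.

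The cost is one more attachment per area, about twice the letter coding, and the loss of some areas that cannot supply last year's letter. The number of non-trial areas is not given, so the size of that loss cannot be stated. If few areas changed their letter, the estimate for outcome ii will be imprecise, but that will then be visible. The randomised trial does not change.
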